Study Objectives	
1. The primary objective is to assess whether the use of a superior hypogastric nerve block performed during uterine artery embolization procedures helps provide better pain management than oral/IV medications alone by assessing patient directed pain scoring and differences in use of oral/IV analgesics
 
2. As secondary objectives the group with the sham procedure and those with the superior hypogastric nerve block will be compared for rate of adverse events, differences in pain/complication related hospital admission/re-admission rates, differences in pain control as related to the bulk volume of fibroids, differences in pain control as related to fibroid disease versus adenomyosis, successful outcome of embolization procedure, successful relief of patient symptoms from the fibroids at time of follow-up

Study Design & Procedure	
This is a prospective double-blinded randomized comparative trial. Experienced interventional radiologists at the MUHC will carry out all intervention.
 
 • 50 consecutive subjects meeting the eligibility criteria, scheduled for uterine artery embolization for symptomatic uterine fibroids and/or adenomyosis. • Consent will be obtained from all patients by a interventional radiologist who will not be involved in the procedure itself. • All procedures will be performed by a qualified interventional radiology medical doctor (IRMD). • Patients who accept to participate and fit the criteria will be randomized to either receive a superior hypogastric nerve block (SHGNB) during the procedure or simply injection of xylocaine in the skin at the periumbilical subcutaneous tissues (sham procedure). • The hypogastric nerve block or sham procedure will be performed by an independent interventional radiologist while the primary operators (radiologists and support staff) of the uterine artery embolization are removed from the room. Once the block or sham procedure is completed, the primary operators returns to the room to

	
complete the uterine artery embolization.
 
 • The patients view of the procedure will be blocked during this time to ensure they are not aware of whether they have had a nerve block or simply a sham procedure • The patient will be offered IV analgesia using midazolam and fentanyl during the procedure at set regular intervals • Similar analgesics as well as per oral analgesics will be provided as per set orders during the recovery period in the post-procedural recovery room • The patient will be discharged home with standard prescriptions for home analgesics which include routine medication and medication to be used for breakthrough pain. • At home, the patient will be filling out an online or paper survey to monitor use of medication and assessment of pain on a visual analogue pain scale. To preserve anonymity of patients deciding to fill out the online survey, the patient will be assigned a anonymous number to be used to log into the survey system prior to leaving the hospital • Data will be gathered, stored, and analyzed. • Follow-up of the patient will occur as per routine 4-6 months post embolization to assess the clinical success of the procedure. 
Subject data collection on the day of the procedure will include demographics, relevant medical history, vital signs, use of IV analgesics, use of oral analgesics, use of SHGNB or sham procedure. Subject data collection while at home will include visual analogue pain scale and self-recording of medication intake.


Study Rationale
	
Uterine fibroids have a significant negative impact on the quality of life of many women who are in their reproductive years. Problems associated with uterine fibroids include excessive blood loss during menstruation (menorrhagia) with often irregular menstrual periods (menometrorrhagia), in some cases leading to marked anemia and need for blood transfusions, excessive pain especially during menstruation (dysmenorrhea), and symptoms of bulk causing compression on the bladder and increased urinary frequency often with waking up at night to urinate (nocturia) or even incontinence, or compression of the rectum causing constipation. As well many women suffer from painful intercourse (dyspareunia), which can have negative impact on self-image and marital status. These symptoms can be very debilitating, and are often career limiting.
 
Until relatively recently, most of these women had to opt for hysterectomy to help control these symptoms. However in the late 1990s, several publications demonstrated the feasibility of uterine artery embolization to control these symptoms. By blocking the blood flow to the fibroids, the fibroids became necrotic and the symptoms resolved. Since then the technique has become widely accepted as a less invasive alternative to surgery with excellent clinical results.

	
The biggest complication of the embolization is that of pain, which is almost universal. The embolized fibroids lead to significant discomfort gradually decreasing over a period of 7-10 days, with most of the discomfort being present in the first 24 hours. Because of this, many centers still routinely admit their patients overnight with patient controlled analgesia or with epidural analgesia catheters in place. However, because of constraints caused by admission availability, many centers are exploring better regimens of analgesia that would allow patients to go home on the same day as the procedure. Here, at the MUHC we have an analgesia protocol that allows approximately 90% of our patients to be discharged home on the same day, often with significant but tolerable discomfort. However there is much room for further pain control improvement to increase the rate of discharge, to improve pain control amongst discharged patients, and to reduce the rates of return visits to the emergency department and re-admissions due to uncontrolled pain while at home.
 
The superior hypogastric nerve plexus is a primary plexus relaying pain information from pelvic structures, including the uterus. A block of this neural plexus is a well-established technique used in cases of chronic pelvic pain such as that caused by pelvic-based cancers. In 2004, a group from Ottawa published a report using this type of nerve block to control the pain associated with UAE. They placed a very small-gauged needle via a periumbilical anterior approach down to the nerve plexus anterior to the lumbosacral vertebral body and injected a long acting anesthetic agent called bupivacaine in the plexus. They reported a significant improvement in pain control with all their patients being able to be discharged and only a very small proportion needing to return to the hospital because of uncontrolled pain. They have had no significant complications attributed to the nerve block procedure itself. However their study was not a formal comparative study.
 
Here at the MUHC, we have used this technique in several patients with promising initial results, but the procedure remains semi-invasive and we believe needs validation especially since pain is such a subjective symptom. This lack of formal validation is probably why the technique is slow to be adopted by other groups. We believe this study will allow a final conclusion regarding the use of this technique in the treatment of uterine fibroids embolization.
 
The goal of the study is to compare the pain sensations patients have and need for analgesics post uterine artery embolization for fibroids by generating a double blinded situation in which neither the patient or primary operator of the embolization are aware of whether the block has been performed or not.


Planned Sample Size
	
Based on published data, the average pain felt by ladies post uterine artery embolization is 7/10 with a standard deviation of approximately 2.5. The published study of SHGNB for UAE demonstrated a decrease in pain from 7 to 2-5 depending on the analgesics regimen used. We

	
opted for the conservative drop in pain scale from 7 to 5 with a standard deviation of 2.5. This gives an effect size of 0.8. With type I error (alpha) set at 0.05 and type II error (beta) set at 0.2 (power of 80%), the sample size calculations yields a needed sample size of 42. We expect up to a 20% drop out rate due to loss to follow-up, giving a total sample size needed of 50, leaving 25 patients per group.
 
Since the pain drop can be more significant than the conservative value we have opted to use, we suggest an interim analysis that would be expected to give us statistical significance if the pain scale was improved by 50% from 7-3.5 (4 being the number usually used by the recovery room to decide to release patients). Based on similar calculations, to show this level of improvement (taking in account a similar drop out rate), one would need a total of 20 patients and therefore we plan on doing an interim analysis at 20 patients having completed the study to see if there is any need to continue the study or not.

Inclusion Criteria	
 1. Women with symptomatic fibroids or adenomyosis that have requested and been approved for uterine artery embolization 2. Age of patients ranging between 35 and 60 years old 3. Ability to comply with the requirements of the study procedures
Exclusion Criteria	
 1. Patients in whom the vascular anatomy prevents access to the superior hypogastric nerve plexus safely 2. Patients who have known allergy to the anesthetic agent 3. Patients with signs of skin infection at the entry site of the needle used to place the nerve block 4. Patients with signs of infection such as fever 5. Patients with history of inflammatory bowel disease or with signs of colitis 6. Patients with uncorrectable abnormal coagulation status (INR >1.5 and plt < 50000 without use of anticoagulation agents) 7. Patients with preexisting conditions, which, in the opinion of the investigator, interfere with the conduct of the study. 8. Patients who are uncooperative, cannot follow instructions, or who is unlikely to comply with follow-up appointments or fill-out the post-procedural pain questionnaires. 9. Patients with mental state that may preclude completion of the study procedure or be unable to provide informed consent
Schedule of Study Visits	
No change from routine schedule presently used:
 
 1) MRI pre-UAE 2) Consultation pre-UAE (consent will be obtained at this time) 3) UAE procedure (not usually the same day as the consultation) 4) MRI 4-6 months post-UAE 5) Consultation post-UAE after post-UAE MRI completed
Efficacy Outcome	
 ▪ Primary: 
 ○ Reduction in pain as measured by patient self administration of visual analogue scale

	
 ○ Reduction in use of oral analgesics at home and IV/oral analgesics while in hospital ▪ Secondary: Comparison of sham versus SHGNB group to look for 
 ○ Differences in adverse events ○ Differences in pain/complication related admissions ○ Differences in pain in relation to total volume of fibroids ○ Differences in pain in relation to fibroids versus adenomyosis ○ Differences in successful outcome of the embolization both by imaging and clinically ○ Use of the online questionnaire vs the paper questionnaire
Safety	
 ▪ Possible adverse events the SHGNB would include: 
 ▪ Infection ▪ Bowel injury ▪ Vascular injury/Bleeding ▪ Pain or nerve injury ▪ Allergic reaction to the anesthetic agent ▪ Intravascular injection of the anesthetic agent which can lead to cardiac arrhythmias or seizures ▪ Hospitalization or emergent surgery 
The rate of significant complications is estimated to be less than 0.5%.
 
In the sham group, the only significant risks would be infection and allergic reaction to the anesthetic agent.
 
 ▪ Expected possible adverse events of the uterine artery embolization, independent of SHGNB or not 
 ▪ Pain ▪ Vascular injury/Bleeding ▪ Embolization material migrating to non-targeted organs ▪ Premature ovarian failure ▪ Uterine infection leading to possible hysterectomy ▪ Pulmonary Embolus ▪ Leaving a uterine sarcoma unresected 
Other than pain, which is almost universal and premature ovarian failure that can occur in 2-10% of patients, the other risks are in the order of 1-2% or less. Other than pain, it is expected that these complications will be independent of whether a SHGNB is

	
performed or not.
 
Subjects with procedure related adverse events will be followed up until the resolution of the event.
 
A medical monitor will analyze all serious adverse events (“SAE”) in order to confirm that they are unrelated to the research protocol.

Statistical Methods	
Descriptive statistics will be provided for the efficacy outcome results and will be presented in terms of percentage, frequency, means and 95% confidence interval. Differences between both groups will be compared using Chi-square test for categorical variables and, after verifying a normal distribution to the data, a Student’s t- test for the continuous variables. Regression analysis will be performed to compare time dependent events.

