1.3. Pain from Uterine artery embolization

When UAE was first started, the need for pain control was evident. Although it was initially done with general anesthesia in the USA, it was quickly found that this was not necessary. However almost everyone admitted the patient overnight with morphine based patient controlled analgesia (PCA). The use of PCA pumps allowed careful assessment of the pain course after UAE. The information gathered shows a maximal pain threshold reached at approximately 2 hours post-procedure, which lasts 3-4 hours and then a gradual decrease to a lower plateau over another 4-6 hours. This period of decrease to a lower pain plateau is the time during which attempts at discharging the patients from the hospital with oral pain medication is attempted [5]. Most women declare no longer having embolization related pain after 7-10 days.

Because of limited availability to hospital admission after radiological procedures at the MUHC, and the need to offer this less invasive treatment of uterine fibroids to women, the interventional radiologists at the MUHC have offered the procedure with an aggressive IV/Oral sedation protocol while in recovery and discharge orders 4-5 hours after the end of the procedure. The patients are sent home with oral pain medication. However despite this aggressive protocol, approximately 5-10% of patients need admission, not without difficulties at times due to the chronic shortage of beds. This is primarily because this time point of attempted home discharge from the recovery room is still in the phase where the lower more tolerable pain plateau, usually reached only approximately 8 hours after the procedure, has not been reached yet. Even in those that are successfully sent home, they report significant discomfort upon discharge from the hospital and there are some that return to the emergency department for pain management.

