accordingly. We expect that the data analysis will consist of regression analysis of the temporal pain level distribution between the group with and without the SHGNB. Continuous variable data, with normal distributions, subgroup analysis of the secondary objectives will be compared using a Student's t- test.

▪ **Sample size calculation**

Sample size calculations are based on published data showing the average pain felt by ladies post uterine artery embolization being of 7/10 with a standard deviation of approximately 2.5. The published study of SHGNB for UAE demonstrated a decrease in pain from 7 to 5-2 depending on the analgesics regimen used [6]. We opted for the conservative drop in pain scale from 7 to 5 with a standard deviation of 2.5. This gives an effect size of 0.8. With type I error (alpha) set at 0.05 and type II error (beta) set at 0.2 (power of 80%), the sample size calculations yields a needed sample size of 42. We expect up to a 20% drop out rate due to loss to follow-up, giving a total sample size needed of 50, leaving 25 patients per group. [8]

If the analysis of the data after recruiting 50 patients is highly suggestive of an effect but without statistical significance, and if the calculations suggest we could get statistical significance by doubling the number of participants, and there have been no significant adverse events from the nerve block, we would increase the number of patients to 100. If adverse events have occurred, the number would not be increased unless approval by the ethics committee.

▪ **Interim analysis**

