7.2. Consent

In this study we would be obtaining written informed consent from all patients. This will be obtained at the time of the first consultation or on the day of the procedure if the patient has had time to read the information package and agrees to it. The consent will be signed outside of the angiography suite and the consent will be obtained by an interventional radiologist at the time of the consultation who will not be involved in the procedure itself. The consent for the embolization will be separate than that for the hypogastric nerve block research project itself.

Table 1: Schedule of Study Procedures

Parameter	Consult up to 3m prior to procedure	Day of the procedure	Time between procedure and follow-up consult	Follow-up consult 4-6 m after procedure
Information package	X			
Informed consent signed	X	or X		
History& exam	X	X		X
Randomization		X		
UAE/block		X		
Recovery with data gathering of time in hospital		X		
Visual pain scale sheets give to patient		X		
Results from visual pain scale sheets gathered from patient			X	or X

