Data integrity will be maintained throughout the study. Logic rules within the database will be used to maximize integrity, and random data validation checks will be performed routinely. The research investigator will review studies and patients' data on a monthly basis to ensure that patient follow-up is proceeding as expected. All cases where the research investigator finds a discrepancy in imaging interpretation or outcome assessment will be reviewed by the Adjudication Committee, consisting of the principal investigators. An independent radiologist from the MUHC will be asked to determine the outcome of a dispute amongst the Adjudication Committee.

8. Data Analysis:

Data will be collected and tabulated using the commercially available JMP10/SAS statistical analysis software (SAS Institute Inc., Cary, NC, USA). Descriptive statistics will be provided for the efficacy outcome results and will be presented in terms of percentage, frequency, means and 95% confidence interval of the means. Differences between both groups will be compared using the Chi-square test for categorical variables and Student's t- test for the continuous variables. ANOVA test and multivariate logistic-regression analysis will be used to compare interplay of more than two variables. Two-tailed p-values of less than 0.05 will be set for statistical significance.

9. Ethical considerations:

Research Ethics approval from the MUHC Research Ethics Board office will be obtained prior to the commencement of the study or related research procedures. All patients will be informed about the data that will be gathered for the study. All patients will have the ability to refuse participating in the study as soon as they are able to evaluate it and give their approval or not. Patients will always be given options to ask questions at any time and questions will be answered in a non-intimidating way so as to try to avoid influencing the patient's decision. At any time, the patient can decide to remove himself from the study. If this is the case, he will receive the standard of care.

No unique patient identifying data will appear on the sheets that will be coded only by study identification number. A key linking the patient name and study identification number will be maintained in a separate database. All datasheets will be kept in a locked, dedicated research office. All computer records will be maintained in a

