Appendix III - At discharge from recovery room

Identification code: _____

Date of UAE: _____ (YY/ MM / DD)

RVH/MGH # _____ Age: _____

Pain scale at time of arrival to recovery (0-10): _____ (time: __:__)

IV Medications used during recovery (Dose/ time/pain scale at time of giving it):

Fentanyl (Dose/Time): _____ ug _____:_____ /10
 _____ ug _____:_____ /10
 _____ ug _____:_____ /10
 _____ ug _____:_____ /10
 _____ ug _____:_____ /10

Midazolam (Dose/Time): _____ mg _____:_____ /10
 _____ mg _____:_____ /10
 _____ mg _____:_____ /10
 _____ mg _____:_____ /10
 _____ mg _____:_____ /10

Other (Name/Dose/Time): _____ :_____ /10
 _____ :_____ /10
 _____ :_____ /10

Oral Medications used during recovery (Dose/time/pain scale at time of giving it):

Empracet: _____ / _____ : _____ / _____ /10
 Tramacet: _____ / _____ : _____ / _____ /10
 Oxycodone: _____ / _____ : _____ / _____ /10
 Hydromorphone: _____ / _____ : _____ / _____ /10
 Naprosyn: _____ / _____ : _____ / _____ /10
 Other: : _____ / _____ : _____ / _____ /10
 _____ / _____ : _____ / _____ /10

Pain scale at departure from recovery (0-10): _____ (time: __:__)

Admission to hospital

No Yes - Why: _____

Complications while in recovery: _____

Patient D/C with antibiotics No
 Yes (Name/Dosage/Frequency x # Days)
_____ / _____ / _____ x _____ d

Patient D/C meds: (Name/Dosage/Frequency x # Days)

- Empracet / _____ / _____ x _____ d
- Tramacet / _____ / _____ x _____ d
- Oxycodone / _____ / _____ x _____ d
- Hydromorphone / _____ / _____ x _____ d
- Naprosyn / _____ / _____ x _____ d

Other: _____ / _____ / _____ x _____ d
_____ / _____ / _____ x _____ d
_____ / _____ / _____ x _____ d

Inform patient how to fill out pain scales at home and how to do it by internet. Give out the sheets but encourage using internet if possible and patient at ease with this.

If willing to use internet:

Get patient email address: _____@_____.

Patient anonymous login name: _____

(first letter of hospital/tree numbers in assigned ID code (Ex if first patient enrolled and at the RVH – anonymous ID # is R001))

Give out their login name for the anonymous internet access and write down on hard copy pain scale sheets that go with patient. Give out hard copy sheets even if patient wants to use internet.

Send email immediately to patient to link to internet forms.

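### Same-day discharge is assessed only through secondary admission and return rates with too few expected events to test, while recovery times already on the forms go unanalysed

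*Combined protocol and SAP*

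**What the plan says.** The Study Rationale in the synopsis gives discharge as a motive: "However there is much room for further pain control improvement to increase the rate of discharge". Section 1.3 describes the local difficulty, that "approximately 5-10% of patients need admission" and that beds are short. Section 4 lists more same-day discharge, if shown, as a further benefit.

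The primary objective is pain score and analgesic use. Discharge enters only through secondary outcomes, and the lists differ:

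- Synopsis, Study Objectives: "differences in pain/complication related hospital admission/re-admission rates".
- Synopsis, Efficacy Outcome: admissions related to pain or complications, with no mention of re-admission.
- Section 3: the same pain/complication item, plus admission rates without restriction by cause, plus emergency-room returns for pain.

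The synopsis gives the test: "Differences between both groups will be compared using Chi-square test for categorical variables". Section 8 repeats it and adds "Two-tailed p-values of less than 0.05 will be set for statistical significance". Section 5 sets "type II error (beta) set at 0.2 (power of 80"%), for the pain score only.

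On data collection, Table 1 lists "Recovery with data gathering of time in hospital". Appendix III has clock-time fields beside the pain score on arrival in recovery and beside "Pain scale at departure from recovery (0-10"), and asks the reason for any admission. No objective or analysis names time in recovery.

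**The concern.** An admission rate of 5-10% in a trial of 25 per group leaves very few events. A yes/no comparison then says almost nothing, whichever test is used. This matters because Section 4 also plans to use a finding of no benefit as grounds for avoiding the block. An uninformative null on admissions could be taken as evidence that the block does not help women go home.

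Two features of the definition make the rate harder to read. Admission and re-admission are combined in the synopsis, although the cited block series (Section 1.4) had 100% discharge followed by 5% re-admission for pain. Pain and complications are also combined, although one is an efficacy matter and the other a safety matter. Meanwhile the forms collect a time for each woman that could describe how recovery went, and nothing is planned with it.

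**Working it through.** **Inputs.** 25 per group, from a total of 50 (Section 5). Two-sided alpha 0.05 (Section 8). Admission without block 5-10% (Section 1.3). Admission with block 0% in the cited uncontrolled series, and 5% re-admission for pain (Section 1.4).

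**The plan's own figure.** The only sample-size calculation is for the pain score: d = (7 - 5)/2.5 = 0.8. A t-test with 80% power needs 21 per group, 42 in all, at one-sided 0.05. At the two-sided level in Section 8 it needs 26 per group, 52 in all. The stated 42 therefore reproduces only one-sided, which is a side matter here. Nothing is calculated for admission.

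**Expected procedure-day admissions.**
- Sham: 25 × 0.05 = 1.25 to 25 × 0.10 = 2.5.
- Both groups, block fully effective: 1.25 to 2.5.
- Both groups, no block effect: 50 × 0.05 = 2.5 to 50 × 0.10 = 5.
- Re-admissions at the cited 5% add 25 × 0.05 = 1.25 in the block group. The documents give no sham re-admission rate.

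Even with 5 events in total, the expected count in each admitted cell is 2.5, below the customary 5 for chi-square.

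**Smallest significant result with no block admissions.** Uncorrected chi-square = N(ad - bc)²/(product of the four margins):
- 3 v 0: 50 × 75²/(25 × 25 × 3 × 47) = 3.19, p = 0.074.
- 4 v 0: 50 × 100²/(25 × 25 × 4 × 46) = 4.35, p = 0.037.

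Fisher's test: 5 v 0 gives p = 0.0502 and 6 v 0 gives p = 0.022. So chi-square needs at least 4 sham admissions and Fisher's test at least 6.

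**Power if the block abolishes admissions.** This is P(X ≥ 4) or P(X ≥ 6) for X ~ Binomial(25, p):

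| Sham rate | Chi-square | Fisher |
|---|---|---|
| 5% | 3.4% | 0.1% |
| 10% | 23.6% | 3.3% |

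If the block instead halves a 10% rate to 5%, exact power is 8% (chi-square) or 1% (Fisher). The chance of no sham admission at all is 0.95²⁵ = 28% at a 5% rate and 0.90²⁵ = 7% at 10%.

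**What would be needed.** For 80% power by the normal approximation, 10% v about 0% needs 74 per group, or 93 with continuity correction. For 5% v about 0% the figures are 153 and 191.

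**How wide the estimate is.** With 0 of 25 block women admitted, the exact 95% upper limit is 1 - 0.025^(1/25) = 13.7%, above the whole 5-10% baseline range.

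**Recovery stay.** The documents give no mean or SD for it, so power in hours cannot be computed. Purely as an illustration, a t-test on a continuous outcome at 25 per group has 79% power for a standardized difference of 0.8. Nothing in the documents says the block has that effect on recovery stay.

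**The case against.** The strongest reply is that admission is a secondary outcome for which the plan claims no power. The trial's stated goal is pain and analgesic use, and discharge is listed only as a further benefit. That stands. A reader might infer that same-day discharge is the trial's real aim and that the design fails it; the documents do not support this.

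A reader might also infer that discharge is examined only through a rate that pools pain with complications. Section 3 contradicts this, since it lists unrestricted admission rates and emergency-room returns for pain. These are still rates with few events.

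A third tempting inference is that complication admissions caused by the block could cancel pain admissions it prevents. The Safety section puts significant block complications below 0.5%. In 25 women that is at most 0.125 expected events, or 1 - 0.995²⁵ = 12% chance of even one, and adverse events are compared separately. The masking risk is close to negligible. Separate reporting is worth having for clarity, not because of it.

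The defence can also argue that recovery time answers a different question. Two women who leave recovery an hour apart both go home the same day, and the problem in Section 1.3 is the few who need a bed. That stands too. If the block changed only admissions and no discharge times, a rank test on recovery stay would have less than 10% power. Discharge orders at 4-5 hours (Section 1.3) and a stay of at least 4 hours (Section 7.4) may also compress the times. Recovery stay therefore cannot replace the admission rate.

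Finally, the synopsis mentions regression for time-dependent events. It names none, and the regression described in Section 5 concerns pain level over time. The option in Section 5 to enlarge to 100 helps only partly. At 50 per group, with admissions abolished, power is 24-75% by chi-square and 4-38% by Fisher's test.

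**Conclusion.** The point holds as a limited, inexpensive improvement to secondary outcomes. At the plan's own admission rate and sample size, the comparison of procedure-day admissions has 3-24% power by chi-square and 0.1-3% by Fisher's test, even against complete abolition of admissions. A non-significant result would carry almost no information about discharge.

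These figures rest on the 5-10% site rate, 25 per group, two-sided 0.05, the uncorrected form of chi-square (the plan does not say which form) and no block admissions, which is the most favourable case. They count procedure-day admissions only. Adding re-admissions raises the event count a little but does not change the conclusion.

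The documents do not support a claim that a recovery-time test would be more powerful. That depends on whether the block speeds recovery in most women or only spares a few an admission, and on a spread of times that is not given. The case for adding it is that the times are already recorded and describe an aspect of discharge the rates cannot.

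**What to change.** Amend the Statistical Methods in the synopsis, Section 3 and Section 8 before unblinding:

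1. Add, alongside the admission rate and not in its place, a secondary analysis of time from arrival in recovery to departure from it (Appendix III clock times), with admitted women ranked last. Use a Wilcoxon test and a Hodges-Lehmann difference with 95% CI. The interval should start at recovery arrival, because no form shown records the end of the procedure.
2. Report admission proportions and their difference with exact confidence intervals, and replace chi-square with an exact test for these sparse counts. State that non-significance will not be read as absence of effect.
3. Report procedure-day admissions by reason (pain, complication) from the reason field on Appendix III, and separately from re-admissions and emergency-room returns. That field covers admission from recovery only, so it cannot classify later returns.
4. Reconcile the three lists of secondary outcomes.

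The cost is analysis wording, with no new data. The downside is that recovery time also reflects logistics, is compressed by the minimum stay, and measures speed of discharge, not whether a bed was needed.
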